2.3 Clinicaltrials.gov

We are currently in communication with the company CellSight Technologies, Inc. ([name] is a founder) that licensed the [¹⁸F]F-AraG patent (US Patent #US20110059014 A1) from Stanford. This company has been clinically evaluating this tracer in parallel to our proposed studies. Toxicity testing and dosimetry has already been performed by the company under FDA IND #123591, and the company has evaluated this tracer in normal subjects prior to testing in cancer patients receiving immunotherapy.

CellSight Technologies has given permission for this study to be submitted to their existing IND 123591.

2.4 Rationale

Benefits: The results may allow for improved, early and sensitive diagnosis of acute GVHD in patients that have undergone a bone marrow transplant. Please refer to pages 6-9 for additional rationale.

2.5 Preliminary results

Please refer to pages 15-22.

2.6 Study Design

Study participants will consist of healthy volunteers for extended studies on radiotracer behavior and patients belonging to a GVHD group. Two patient categories exist within the GVHD group-those highly suspected to have acute GVHD and those that are at high risk for developing acute GVHD. We will recruit healthy volunteers through local advertising. We will recruit high risk and confirmed GvHD patients from the Bone Marrow and Transplantation Clinic at the Stanford Cancer Institute.

Normal subjects will be recruited by publicly disseminating the information about the clinical trial through printed media such as a flyer, or by sending out an email to the Stanford community. We will ask for volunteers. A consent form for healthy volunteers is also included. Patients will undergo preliminary evaluation to ensure eligibility, receive and sign an informed consent, be enrolled in the trial, and then have [¹⁸F]F-AraG PET/CT.

Highly suspected acute GVHD patients will be scanned following biopsy (taken to confirm acute GVHD). The staging and grading of the disease using the Glucksberg grade and International bone marrow Transplant Registry Severity Index (IBMTR) at time of enrollment will be noted. Their consent for a PET-CT scan will be obtained prior to biopsy. Biopsy tissues of consented patients will be analyzed further for T cell involvement.

High-risk patients (recipients of myeloablative or reduced intensity allogeneic transplants using either bone marrow or peripheral blood stem cells from HLA-matched or HLA-mismatched related or unrelated donors-protocols 9917, 9142, 9022, 9924) will have to sign consent forms

before they undergo a transplant. All those that consent will undergo a PET-CT scan day 4 \pm 2 days post transplant. Additionally these patients will be scanned again between day 14-21 post transplant. Follow up on these patients will note those that go on to develop aGVHD and the clinical end point will be correlated to the scans to verify any predictive potential of the radiotracer.

For both GVHD groups-results of the scan will be compared to biopsy results and immunohistochemical staining of the biopsy samples for T cells.

Investigational agent: $[^{18}\text{F}]\text{F-AraG}$ will be formulated in a sterile and pyrogen-free isotonic solution will be administered in a single slow IV injection.

This clinical study will be funded by the Parker Institute of Cancer Immunotherapy at Stanford Medicine Bench to Bedside Program 2017.

Additional resources and costs will be supplemented with the NIH RO1 grant 'A Novel Positron Emission Tomography Strategy for Early Detection and Treatment Monitoring of Graft-Versus-Host Disease' (Grant number 5RO1CA201719-02).

This is a single-arm prospective study of imaging of aGVHD where no randomization will be done (please see section 10 for more information on statistical analysis).

3 PARTICIPANT SELECTION AND ENROLLMENT PROCEDURES

3.1 Inclusion Criteria

This study will enroll three cohorts of participants: healthy volunteers, patients highly suspected to have acute GVHD and requiring systemic therapy, and patients at high risk for developing acute GVHD. For patients highly suspected to have acute GVHD and requiring systemic therapy, biopsy of involved tissue is encouraged to support the clinical diagnosis- this will normally be taken from the gastrointestinal tract. T cell staining will be incorporated in the immunohistochemical analysis of the tissue.

Participants must meet all of the following relevant criteria to participate:

1. Must be 21 years of age or older.
2. Must understand and voluntarily have signed an Informed Consent after its contents have been fully explained.
 - a. For patients highly suspected to have acute GVHD and requiring systemic therapy, informed consent should be signed prior to biopsy taken to support clinical diagnosis.
 - b. For patients at high risk for developing acute GVHD, informed consent should be signed prior to transplant.
3. For healthy volunteers only: Must have no known medical problems that would make undergoing the scan hazardous to the health of the patient or interfere with the results. In particular subjects should not have any cardiac or immunological disorders as these would likely affect the scan results. Subjects should have had a full physical exam within 6 months of the study. If healthy volunteers have not had a full medical exam within 6 months of the study, one of the nuclear medicine physicians will conduct the medical exam prior to any study procedures.
4. For patients highly suspected to have acute GVHD and requiring systemic therapy only:

Taking steroid treatment for suspected acute GVHD for 7 days or less.

5. For patients at high risk for developing acute GVHD only: Recipients of myeloablative or reduced intensity allogeneic transplants using either bone marrow or peripheral blood stem cells from HLA-matched or HLA-mismatched related or unrelated donors (protocols 9917, 9142, 9022, 9924) who have not yet been placed on any therapy for acute GVHD.

3.2 Exclusion Criteria

To participate in this study, subjects must have none of the relevant criteria:

1. Pregnant or nursing
2. Individuals with known or suspected substance abuse, obtained by self-reporting.
3. Uncontrolled infection
4. Relapsed/persistent malignancy
5. Currently receiving immunotherapy

3.3 Informed Consent Process

All participants will be provided a consent form describing the study with sufficient information for participants to make an informed decision regarding their participation. Participants will sign the IRB approved informed consent prior to participation in any study specific procedure. The participant will receive, as is mandatory, a copy of the signed and dated consent document. The original signed copy of the consent document will be retained in the medical record or research file.

3.4 Randomization Procedures

Patients will not be randomized.

3.5 Study Timeline

3.5.1 Primary Completion:

The study will reach primary completion 24 months from the time the study opens to accrual.

3.6 Study Completion:

The study will reach study completion 36 months from the time the study opens to accrual.

4 IMAGING AGENT/DEVICE/PROCEDURE INFORMATION

4.1 $[18\text{F}]\text{F-AraG}$: 2'-deoxy-2'-[18F]fluoro-9- β -D-arabinofuranosyl guanine

The imaging agent to be used in this study is 2'-deoxy-2'-[18F]fluoro-9- β -D-arabinofuranosyl guanine. The radionuclide on this imaging agent being Fluorine-18 (^{18}F). The imaging agent will be administered intravenously.

Clinical grade imaging agent will be synthesized under GMP/GLP conditions at the Lucas Center Cyclotron and Radiochemistry facility, part of the Molecular Imaging Program at Stanford. The imaging agent will be requested as and when subjects become available. The radiotracer will be received at the Nuclear Medicine department at Stanford Hospital in a lead shielded container by an authorized person and with the appropriate transfer sheet.

Dosimetry of this imaging agent has previously been characterized in male and female healthy subjects and the information is included on page 21. Dosimetric calculations were performed

using the OLINDA/EXM 1.1 software using methods previously described using other tracers [Yaghoubi, 2001].

PET/CT is a well established, FDA approved clinical imaging procedure. Each subject will be scanned a maximum of 2 times. For each imaging session the amount of radioactivity that will be administered will be less than 5.7 and 4.4 mCi for males and females respectively.

5 STUDY PROCEDURES

5.1 Imaging Protocol for Patient Groups

Each subject may have up to two imaging sessions. The procedures for each imaging session is detailed below:

Day 1 (Imaging Day)

Overview of procedures prior and post injection of [¹⁸F] F-AraG:

1. Subject will participate in an informed consent session (approximately 30 minutes) and if she/he would like to continue after being fully informed she/he will sign consent form.
2. Subject will be asked to drink several glasses of water before arriving at the nuclear medicine clinic and during the study.
3. Subject will be interviewed to obtain medical history.
4. Volunteer height and weight will be measured.
5. Baseline Heart Rate (HR), Blood Pressure (BP), Blood Oxygen %, Temperature, and Respiratory Rate will be collected at baseline (5-120 minutes prior to the injection of the tracer).
6. IV line may be placed in both arms of healthy subjects for PET tracer injection and another may be used for blood collection. The GVHD patients will have double lumen catheters which can these be used for these purposes.
7. For baseline CBC analysis- 3 ml of blood will be collected and 5 ml of blood will be collected for baseline metabolic panel analysis.
8. Subject may either be positioned on the PET/CT scanner bed or another bed in the clinic (where possible the same PET-CT system should be used especially for the healthy subjects).
9. Injection of [¹⁸F] F-AraG and post-injection procedures will follow.
10. If possible, subjects should be asked to urinate prior to the start of the PET/CT scans.
11. A bolus < 5.7 mCi of clinical grade [¹⁸F] F-AraG for male volunteers or < 4.4 mCi of clinical grade [¹⁸F]F-AraG for female volunteers will be injected through IV.
12. A CT image will be acquired with the PET images.
13. The PET scanning procedure may start at the time of tracer injection or at a later time point after tracer injection. The imaging field includes the vertex to thigh for healthy subjects and vertex to feet for GVHD patients. Up to two whole-body PET scans may be performed at various time points after injection of the tracer, not to exceed 2 hours after tracer injection.
14. Blood pressure, Temperature, Blood Oxygen saturation, Heart Rate, Respiratory Rate will be measured immediately after [¹⁸F]F-AraG PET-CT procedure.
15. A safety follow up will happen at one time point within the time interval (day 2 – day 7) post-scan.
16. All observed adverse events and subject complaints will be recorded.

Healthy subject protocol

1. Volunteer will be asked to drink 1-2 glasses of water before his/her arrival at the clinic.
2. Volunteer will be consented by a member of the study team
3. Female subjects will have a urine or serum pregnancy test to rule out pregnancy.
4. Subject will be weighed.
5. Subject will have an IV line placed in a hand or arm vein for tracer administration.
6. Subject will have an IV line placed in a hand or arm vein for blood sampling.
 - Subject will have a second IV line placed in the vein of the other hand/arm for venous/hand warmed arterialized-venous blood or in a radial artery for arterial blood sampling for kinetic and radio-metabolite analysis, over the first 90 minutes post tracer injection. The arterial/venous or arterialized-venous blood will be sampled in heparinized coated tubes pre-tracer injection and at 1, 3, 5, 10, 15, 30, 45, 60 and 90 minutes post tracer injection (10 sampling points).
 - During this time, care should be taken to prevent movement in the subject from his or her original position in the scanner. The blood sampling volume will be 3 mL, (2mL for whole blood and plasma radioactivity analysis + 1mL for radiometabolite analysis). The exact time point of the collection of each blood sample will be recorded using the same clock device. If an automated blood-sampling device is available (e.g., Twilite system from Swisstrace GmbH) it should be used for the blood sampling procedure, but if this is not available, then the sampling will be done manually.
 - **Radioactivity analysis of whole blood and plasma:** The blood tubes should be weighed before and after collecting the blood. Whole blood radioactivity will be measured. To measure plasma radioactivity, the whole blood samples will be centrifuged. The radiolabeled tracer concentration in whole blood, plasma and pellet will be measured by a gamma well counter (1-min per sample). The counting rates measured by the well counter will be converted to the PET equivalent counts using a conversion factor from a weekly phantom cylinder study. The counts should be decay corrected back to the injection time.
7. Blood pressure, temperature, respiratory rate, heart rate and pulse oximetry measurements will be taken at baseline.
8. A blood sample will be taken prior to the injection of the tracer, to be used for baseline chemistry and hematology laboratory testing (hematocrit should be an included measure).
9. Participant will have EKG leads placed for cardiac gating and then be placed in the scanner.
10. A low dose attenuation correction CT scan (ACCT) of the heart will be performed for attenuation correction.
11. A small low activity calibration source of known activity, volume, and concentration of F-18 activity will be taped to the furthest corner of the scanner field of view prior to radiopharmaceutical injection. The 30 minute dynamic PET acquisition of the heart will then begin, making sure that the entire heart region is covered in the field of view. All PET/CT scans should be done on the Discovery MI PET/CT scanner or the PET/CT 690 scanner.
12. Right after the start of the PET acquisition, [¹⁸F]F-AraG formulated in a sterile and pyrogen-free isotonic solution in less than 10 ml will be administered in a single slow IV injection. The line will be slowly flushed at a constant rate with at least 10 ml normal saline after injection.
13. The initial 5 minutes of the dynamic PET scan will be finely acquired at 5 seconds/frame (total number of frames in initial 5 minutes =60 frames) so as to capture the peak of the cardiac input function and then 1 minute/frame for the next 25 min over the same field of view (FOV). The dynamic PET data should be collected in list-mode and saved

appropriately.

14. Participants will have skull base-to-thigh static PET-CT scans (which includes the brain) obtained again at 60 and 90 minutes (scans #2 and #3). CT will use 120 kV and dose modulation based on body habitus, ranging 10-105 mA for both scans.
15. Blood pressure, temperature, respiratory rate, heart rate and pulse oximetry measurements will be performed post scan 3.
16. All recordings of important time measurements (e.g. time of injection and acquisitions) will be done using the same clock e.g. a phone.
17. Participants will be asked to void frequently to reduce radiation exposure.
18. Adverse drug events that have developed during the scans will be recorded in source documents. Any that develop after $[^{18}\text{F}]\text{F-AraG}$ injection will also be recorded in the source documents when patients seen at the safety follow-up visit at one time point within the time interval (day 2 – day 7) post-scan.
19. After $[^{18}\text{F}]\text{F-AraG}$ injection, participants will be asked to return to the clinic for a safety follow-up visit for blood sample collection for blood chemistry and hematology and also for measurements of vital signs. Results will be recorded in the case report form.

GVHD patient protocol

1. Subject will be asked to drink 1-2 glasses of water before his/her arrival at the clinic.
2. Subject will be consented by a member of the study team
3. Subject will be weighed.
4. The subject will likely have an existing port (double lumen catheters) for administration of the radiotracer.
5. A blood sample will be taken 5-120 minutes prior to the injection of the tracer, to be used for baseline chemistry and hematology laboratory testing. Blood pressure, temperature, heart rate and pulse oximetry measurements will also be taken up between 5-120 minutes prior to injection (baseline).
6. $[^{18}\text{F}]\text{F-AraG}$ formulated in a sterile and pyrogen-free isotonic solution will be administered in a single slow IV injection. The line will be flushed with at least 10 ml normal saline after injection. The bed strap should be open until scanning starts.
7. A small low activity calibration source of known activity of F-18 will be placed in the field of view in each image collected
8. Participants will have a static PET scan at 60 minutes after injection of $[^{18}\text{F}]\text{F-AraG}$ covering all positions from vertex to toe. Attenuation correction will be done with a CT scan (120 kv, 10 mA) usually acquired before the PET scan. There will be 8 bed positions covering head to toe (each position will take approximately 3 minutes). The data should be collected in list mode and saved. Patients that are able to tolerate longer times in the scanner will also undergo an additional scans following the same format described above at 30 minutes post tracer injection.
9. All recordings of important time measurements (e.g. time of injection and acquisitions) will be done using the same clock e.g. a phone.
10. Blood pressure, temperature, respiratory rate, heart rate and pulse oximetry measurements will be taken immediately after the $[^{18}\text{F}]\text{F-AraG}$ PET-CT scan.
11. Participants will be asked to void as frequently as possible to reduce radiation exposure.
12. Participants will be given a copy of the consent form they signed and will be dismissed.
13. Participants will undergo a safety follow-up at one time point within the time interval (day 2 – day 7) post-scan for blood sample collection for blood chemistry and hematology and also for observation for vital signs. For in-patients we will use the blood samples and vital signs

obtained as part of the standard of care by the Bone Marrow and Transplant group. Out-patients will have to return to the clinic for the safety follow up.

14. Adverse drug events will be recorded at one time point with the time interval of 2-7 days after [¹⁸F]F-AraG injection/scan in the case report form.
15. Patients in the high risk of developing GVHD arm will undergo the above protocol once more 10-17 days after the first scan.
16. A post safety follow up will be conducted for up to 6 months via chart review to assess progression or development of aGVHD.

Safety Follow-up [range: One time point within the interval (Day 2 to Day 7) post-scan

1. BP, HR, Temperature, Blood Oxygen %, and Respiratory Rate will be recorded.
2. Blood will be collected for CBC, and Metabolite Analysis.
3. Adverse events will be collected at one time point within the time interval (day 2 – day 7) post scan.

Healthy subjects and out-patients will need to come in to the clinic for the safety follow up. For in-patients (GVHD group)-we will obtain the blood samples and vital signs obtained as part of the standard of care by the Bone Marrow and Transplant group.

Subjects with suspected acute GVHD OR at high-risk of aGVHD will be followed for 6 months post their last scan to evaluate disease (progression/development) by chart-review.

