9.1.1 Primary Outcome Measurement Methods

Static images acquired will be used to determine the bio-distribution of the imaging agent in the GVHD groups. Past images as well as newly acquired data from healthy subjects will be used as comparisons. Regions of interest will be drawn on various organs such as the liver, cervical lymph nodes and gut and quantified using imaging software (e.g. Inveon Research Workplace or Amide). In addition any areas that show up differently in the GVHD groups, to the normal bio-distribution seen in healthy subjects will be identified and ROIs will also be drawn over these regions.

Bio-distribution data will be expressed as % injected dose/gram (%ID/g) and/or as standard uptake values (SUV) with respect to the organ being studied. In the high suspected aGVHD group, [¹⁸F]F-AraG PET results will be compared to any grades and scores of aGVHD severity attributed to subjects. In the case of the high-risk group, after the second scan, patients will be monitored for development of aGVHD and the clinical endpoint (whether or not the high risk patient develop aGVHD) will represent the primary outcome variable. In addition, IHC analysis of biopsies taken in either GVHD group will help in the interpretation of the primary results and thus potentially support interpretation of the PET data. The IHC analysis will involve determining the amount of cell death or T cell infiltration and activation.

Vital signs and blood laboratory data collected before and after the i.v. injection of [¹⁸F]F-AraG will allow evaluation of any unexpected side effects.

To measure plasma radioactivity, whole blood sample will be centrifuged. The radiolabeled tracer concentration in whole blood, pellet post centrifugation and plasma will be measured by a gamma well counter (1-min per sample). The counting rates measured by the well counter will be converted to the PET equivalent counts using a conversion factor from a weekly phantom cylinder study. The counts should be decay corrected back to the injection time.

Plasma parent tracer and metabolite concentrations will be determined using solid phase extraction combined with HPLC technology.

Clinical assessment of disease severity will be made by the aGVHD grade. Staging and grading of the disease will be performed by Clinicians at the Bone Marrow and Transplant Clinic using the Glucksberg grade and International bone marrow Transplant Registry Severity Index (IBMTR) at time of enrollment and imaging.

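### No vital signs are scheduled between injection and the end of scanning (about 84 minutes in GVHD patients, beyond 90 in volunteers), so a brief, symptom-free change would not appear in the vital-sign data

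*Combined protocol and SAP*

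**What the plan says.** Section 5.1 holds a general list of steps, a healthy subject protocol and a GVHD patient protocol.

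- **GVHD baseline (GVHD protocol, step 5):** "Blood pressure, temperature, heart rate and pulse oximetry measurements will also be taken up between 5-120 minutes prior to injection (baseline").
- **GVHD scan (step 8):** "Participants will have a static PET scan at 60 minutes after injection of" the tracer, and "There will be 8 bed positions covering head to toe (each position will take approximately 3 minutes"). An earlier scan, timed in minutes after injection, is optional: "Patients that are able to tolerate longer times in the scanner will also undergo an additional scans following the same format described above at 30".
- **GVHD post-injection set (step 10):** "Blood pressure, temperature, respiratory rate, heart rate and pulse oximetry measurements will be taken immediately after the" PET-CT scan.
- **Volunteers (healthy subject protocol, steps 14-15):** static scans are "obtained again at 60 and 90 minutes (scans #2 and #3"), and "Blood pressure, temperature, respiratory rate, heart rate and pulse oximetry measurements will be performed post scan 3".
- **General list, step 14:** the set is likewise taken directly after the PET-CT procedure.
- **Tables 6-1 to 6-3:** the vital-signs row is empty in the injection columns and marked in the post-injection columns, with no clock time.

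Section 9.1.1 states the purpose: vital signs and blood results from before and after the injection "will allow evaluation of any unexpected side effects". Section 1.2 makes toxicity in GVHD patients a secondary objective.

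**The concern.** The plan gives the before-and-after vital signs a safety purpose, but the after reading comes well over an hour after injection. A change in pressure, heart rate or saturation that starts at injection and resolves within that time, without symptoms, lies wholly inside an interval with no scheduled reading. A table showing no change from baseline could then be read as evidence of no acute effect, when it speaks only to the state at about 84 or more than 90 minutes.

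This matters somewhat more because section 10.7 describes the study as the first use in GVHD patients. Section 7.1 also lists hypotension, hypertension, hypoxia, tachycardia and fever as expected after transplant, and section 7.2 logs non-serious events only if they are attributed to the agent or a study procedure, or lead to withdrawal. Without a reading close to injection, there is little objective basis for attributing a transient change.

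**Working it through.** The documents state no time from injection to the next vital signs, so there is no figure of the plan's own to reproduce. The interval has to be built from the schedule.

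**1. GVHD patients.** Inputs from the GVHD patient protocol: scan at 60 minutes (step 8), 8 positions of about 3 minutes (step 8), vital signs directly afterwards (step 10).

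- Scan length: 8 x 3 = 24 minutes.
- Injection to vital signs: 60 + 24 = about 84 minutes.
- The 3 minutes is approximate. Assuming 2.5 to 3.5 minutes per position gives 60 + 20 = 80 to 60 + 28 = 88 minutes.
- The optional scan would end at about 30 + 24 = 54 minutes, but no vital signs are attached to it.
- With baseline 5-120 minutes before injection, the two sets are 5 + 84 = 89 to 120 + 84 = 204 minutes apart.

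**2. Volunteers.** The set follows scan 3, which starts at 90 minutes. The length of scan 3 is not stated, so the interval is more than 90 minutes.

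**3. Could the general list bring the reading forward?** Step 13 of that list lets scanning start at injection, and a single 24-minute scan begun then would end at about 24 minutes. But step 8 of the GVHD protocol and footnote e of Tables 6-2 and 6-3 fix the required scan at 60 minutes, so about 84 minutes stands for those patients.

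**4. Illustration of what timing does.** Assume a change starts at injection and lasts an exponentially distributed time with mean m. Neither assumption comes from the documents. The chance that it is still present at time t is exp(-t/m).

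| Reading at | m = 15 min | m = 30 min | m = 60 min |
|---|---|---|---|
| 10 min | 51% | 72% | 85% |
| 30 min | 14% | 37% | 61% |
| 84 min | 0.4% | 6% | 25% |

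These figures are conditional on a change occurring. They say nothing about how often one would.

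**5. Prior exposure.** Section 7.1 gives 6 + 3 + 2 + 3 = 14 people, with only mild side effects. Zero worse-than-mild events in 14 has an exact one-sided 95% upper bound of 1 - 0.05^(1/14) = about 19%. This is reassuring but limited, and none of the 14 is described as a GVHD patient.

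**The case against.** The strongest reply is that the plan does what section 9.1.1 says: it measures before and after injection. No section promises a reading near the injection, and section 10 plans no vital-sign inference that could be biased. This stands, and it is why the point is an improvement and not a contradiction.

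A reader might infer that a short reaction would leave no trace at all. The documents do not support that. The general list (step 16) has observed events and complaints recorded, step 18 of the healthy subject protocol covers events during the scans, and all three study calendars mark adverse event evaluation on the day of injection. Volunteers also wear EKG leads, for cardiac gating, which could show a change in heart rate. What goes unmeasured is a change that is brief, without symptoms and unnoticed. None of these routes, however, supplies a scheduled blood pressure or saturation reading in the interval, and Tables 6-2 and 6-3 list no EKG for GVHD patients.

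A reader might also infer that such reactions are to be expected. The documents give no such signal: section 2.2 puts the tracer at nanogram-to-microgram mass and reports no treatment-related findings in rats, and section 7.1 reports only mild effects. This lowers the urgency.

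It is also fair that an early reading in volunteers is harder to take. The healthy subject protocol places lines in both arms and asks that movement be prevented while blood is sampled, so a set during the dynamic scan could disturb the input-function data. In the illustration above, a reading at 30 minutes would still miss 86% of changes with a mean duration of 15 minutes.

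Finally, step 5 of the GVHD protocol leaves respiratory rate out of the baseline although step 10 measures it after the scan. One might conclude that its change from baseline cannot be computed. But step 5 of the general list requires it at baseline, so this is a wording slip to reconcile.

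**Conclusion.** The concern holds in a limited form. The only same-day post-injection vital signs come at about 84 minutes in GVHD patients (80-88 if a position takes 2.5-3.5 minutes) and after 90 minutes in volunteers. A brief, symptom-free change would not appear in the vital-sign data that section 9.1.1 relies on, while visible or reported reactions remain covered. The 84 minutes is an approximation, not a guaranteed minimum, and assumes that the GVHD-specific steps govern over the flexible start in the general list. The percentages by duration illustrate timing only, since the documents give neither durations nor incidence. No stated figure is wrong and the primary analysis is unaffected. The gap is worth closing in GVHD patients because toxicity there is a secondary objective and one added reading per session closes most of it.

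**What to change.** **GVHD patients.** Add one set of vital signs about 5-15 minutes after injection. They are not due on the scanner before 30 minutes (optional scan) or 60 minutes (required scan), so this fits before any scan starts. Keep the post-scan set, add the new time to Tables 6-2 and 6-3, and summarise change from baseline at both times.

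**Volunteers.** An added set is optional. If taken, place it between the end of the dynamic scan (30 minutes) and scan 2 (60 minutes), away from the 45-minute blood sample and without repositioning the subject, and update Table 6-1. Otherwise, state in the report that the vital signs do not cover the first 90 minutes.

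**Wording.** Reconcile step 5 of the GVHD protocol with step 5 of the general list so that respiratory rate is part of the GVHD baseline.

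**Cost.** A few minutes of staff already present and one more case report form row per session, with no extra visit, blood sample or radiation.
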